Visit Plan	For patients under treatment and follow-up at this hospital, no in-person visits are required; relevant data can be obtained from the electronic medical record (EMR) system and imaging system of this hospital. For patients not receiving treatment at this hospital, a telephone follow-up protocol is implemented to obtain relevant pathological results.

research report	The study plans to enroll 120 eligible patients within 3 years, followed up their pathological results, and conduct statistical analysis.
statistical analysis	Statistical analysis was performed using SPSS 17.0. The diagnostic sensitivity, specificity, and negative/positive predictive values were calculated using a four-cell table. The area under the ROC curve and the optimal cutoff value (SUV optimal cutoff) were evaluated by ROC curve analysis. The consistency between 18F-FAPI PET diagnosis and pathological diagnosis was assessed using the kappa test. A p-value <0.05 was defined as statistically significant.

English abbreviation reference

PET	Positron emission tomography
CT	Computed tomography
ROC	Receiver operating characteristic curve
FAPI	Fibroblast activation protein inhibitor

1 Research Background

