5.2.2 Clinical Indicator Assessment

The gold standard is the pathological result of biopsy or surgery.

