5.3 Subject Selection

5.3.1 Eligibility Criteria for Subjects

- (1) Patients with suspected or confirmed lung cancer
- (2) 18F-FAPI PET/CT has been performed.

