5.4 Study Endpoints

Primary endpoint: Diagnostic efficacy of 18F-FAPI PET/CT in lung cancer patients (sensitivity, specificity, accuracy)

secondary end points:

- ① Compare the diagnostic performance differences of 18F-FAPI PET/CT with CT, MR, and 18F-FDG PET imaging in clinical applications for lung cancer;
- ② Analysis of diagnostic differences in the subgroup of patients (pathological, genetic, etc.) using 18F-FAPI PET/CT;
- ③ Evaluation of 18F-FAPI PET/CT in predicting lung cancer prognosis.

6 Research Procedures and Operational Standards

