6.2 Subject Screening

Participants will sign an informed consent form prior to enrollment in this study. Investigators will explain the nature, purpose, and risks of the study and provide the participants with an informed consent form. Participants will be given sufficient time to consider the significance of the study before deciding whether to participate. Any modifications to the informed consent form must be notified and approved by the ethics committee prior to participant enrollment.

First, participants must undergo an informed consent process and sign an informed consent form. Subsequently, eligible subjects are screened from the target population according to the pre-established inclusion and exclusion criteria of this study, after which they may be considered for inclusion in the research.

Baseline data collection included general examinations, medical history, and laboratory tests conducted at the same hospital or external hospitals within one week prior to the signing of the informed consent form. Adverse events and concomitant medications were collected after the signing of the informed consent form.

history-taking

Conduct a detailed inquiry into the patient's medical history to clarify symptoms, signs, and prior medical history (e.g., tumor history, surgical history, biopsy history, radiotherapy history, chemotherapy history, family history,

allergy history, etc.), relevant laboratory tests, previous imaging findings (including plain radiography, ultrasound, CT, MRI, as well as 18F-FDG PET/CT, PET/MR, etc.), and recent pathological results (including tumor grading and Ki-67 index, etc.), along with the patient's follow-up medical records.

Image judgment criteria

The uptake of imaging agents in tissues or organs that normally do not take up such agents can be considered pathological. Typically, 18F-FAPI is rapidly cleared from the bloodstream. Taking 18F-FAPI as an example, radioactive distribution can be observed in the salivary glands, thyroid, liver, biliary tract, gallbladder, pancreas, adrenal glands, kidneys, intestines, collecting system, and bladder, with almost complete excretion through the biliary tract. There is minimal distribution of the radioactive imaging agent in brain tissue. Compared to the liver, if the uptake is significantly increased in a lesion, it is considered positive, suggesting malignant tumors. Generally, moderate intestinal distribution and non-focal intestinal uptake are considered non-pathological.

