7.1 Total Sample Size

Assuming we obtained the sensitivity (Se) of 0.92, specificity (Se) of 0.96, and disease prevalence (P) of 0.05 from the literature [9-11], we set the allowable error (d) to 0.08, with a confidence level of 95% (Z=1.96). When estimating the sample size using sensitivity, the formula yields

$$N = (1.962 * 0.95 * (1 - 0.95)) / 0.052 = 113$$

The sample size was estimated to be 113 cases according to theoretical calculation.

In addition, based on previous studies, the potential loss-to-follow-up rate for patients is estimated to be 5%-10%. This study anticipates a 10% loss-to-follow-up rate during the clinical trial, with a calculated total sample size of 120 cases. This is a multicenter study, with 80 cases from our center (The First Affiliated Hospital of Zhejiang University School of Medicine), 20 cases from Zhejiang Provincial People's Hospital, and 20 cases from Shulan Hangzhou Hospital.

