7.3 Statistical Methods

Statistical analysis was performed using SPSS 17.0. The diagnostic sensitivity, specificity, and negative/positive predictive values were calculated using a four-cell table. The area under the ROC curve and the optimal cutoff value (SUV optimal cutoff) were evaluated by ROC curve analysis. The consistency between 18F-FAPI PET/CT diagnosis and pathological diagnosis was assessed using the kappa test. A p-value <0.05 was defined as statistically significant.

Statistical analysis was performed using SPSS 17.0.

① Diagnostic performance evaluation, four-grid table index calculation:

Sensitivity = True positives / (True positives + False negatives) × 100%

Specificity = True Negative / (True Negative + False Positive) × 100%

Positive predictive value = true positive / (true positive + false positive)

Negative predictive value = true negative / (true negative + false negative)

② ROC curve analysis:

Calculate the area under the curve (AUC) and evaluate diagnostic performance (AUC>0.9 indicates excellent, 0.8-0.9 indicates good, 0.7-0.8 indicates moderate).

Determine the optimal cutoff for SUV using the maximum Youden index.

③ consistency check

The consistency between 18F-FAPI PET/CT and pathological diagnosis was evaluated using the Kappa coefficient.

Kappa>0.8: Excellent consistency;

0.6-0.8: High consistency;

<0.6: Consistency should be interpreted with caution.

Bilateral test, $p<0.05$ defined as significant difference.

④ survival analysis

Kaplan-Meier method:

Collect baseline PET parameters (lesion SUVmax, lesion SUVmean, MTV, LTV, bone marrow SUVmax, etc.), and plot PFS/OS curves according to treatment response (CR/PR vs. SD/PD), pathological response (e.g., MPR status), or PET parameter grouping (e.g., high/low SUVmax). Compare the significance of survival differences between groups using the Log-rank test ($p<0.05$).

Cox proportional hazards model:

Univariate analysis: Screening of clinical variables associated with PFS/OS (age, stage, SUVmax, MTV, etc.).

Multivariate analysis: Significant univariate variables ($p<0.1$) were included, with quantified hazard ratios (HR) and 95% confidence intervals.

Verify the proportional hazards assumption (Schoenfeld residual test).

8 Data Recording and Management

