8.1 Investigator Data Records

- 1) For all eligible participants who have signed the informed consent form, their relevant data and laboratory test results must be meticulously and thoroughly documented.
- 2) All imaging data were interpreted by two attending physicians with over 5 years of experience in nuclear medicine, and the chief physician provided the final consensus interpretation for any questionable cases.
- 3) Original data records, signed by the investigator and dated.

4) Confirm that all adverse events have been documented, and that serious adverse events have been reported and recorded in accordance with relevant procedures in a timely manner.

9 Expected Research Progress

Study recruitment period: 36 months

Observational study duration: This study was an observational study, with patient mortality serving as the endpoint of follow-up.

10 Adverse Event Assessment and Reporting

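### The reference standard puts biopsy and surgery on equal terms and does not confirm a non-malignant biopsy, so a missed cancer can be counted as reference-negative

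*Protocol*

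**What the plan says.** The definition of the reference standard is one sentence in Protocol 5.2.2, under the heading on reducing bias: "The gold standard is the pathological result of biopsy or surgery". Nothing elsewhere ranks surgery above biopsy, says what to do with a non-diagnostic sample, or requires a non-malignant biopsy to be confirmed.

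The surrounding provisions are:

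- **Eligibility (5.3.1):** "Patients with suspected or confirmed lung cancer". A patient already confirmed cannot become reference-negative through a missed biopsy; a suspected patient can.
- **Primary endpoint (5.4):** "Primary endpoint: Diagnostic efficacy of 18F-FAPI PET/CT in lung cancer patients (sensitivity, specificity, accuracy").
- **Scoring (7.3):** "Specificity = True Negative / (True Negative + False Positive) × 100"%. A scan-positive patient with a non-malignant reference result is therefore a false positive.
- **Scan positivity (6.2):** "Compared to the liver, if the uptake is significantly increased in a lesion, it is considered positive, suggesting malignant tumors".
- **Follow-up for diagnosis (synopsis, Visit Plan):** patients treated at the hospital are followed through its records. For the others, "a telephone follow-up protocol is implemented to obtain relevant pathological results".
- **Length of follow-up (Section 9):** "This study was an observational study, with patient mortality serving as the endpoint of follow-up". This is not linked to the reference standard.

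**The concern.** A malignant biopsy is close to conclusive. A non-malignant biopsy of a suspicious lesion is weaker evidence, because the needle can miss the tumour. Under 5.2.2 such a result meets the standard as fully as a resection does. A cancer missed by sampling can then sit among the reference-negatives, and a correct positive scan in that patient is scored as an error.

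The same label feeds all three primary measures, and also the predictive values, kappa, the ROC area and the Youden cutoff in 7.3. The error is systematic, so enrolling more patients would not reduce it.

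A second gap is discordance. If a benign biopsy is followed by a malignant resection, both satisfy 5.2.2 and no rule says which prevails. Section 5.2.1 specifies no blinding, so that choice could be made with the FAPI result known.

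This point concerns patients who do have tissue. Scan-negative patients who never have tissue taken are a different issue.

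**Working it through.** **Inputs from the Protocol (7.1).** "Assuming we obtained the sensitivity (Se) of 0.92, specificity (Se) of 0.96, and disease prevalence (P) of 0.05 from the literature"; allowable error 0.08. The plan gives no figure for reference-standard error, so there is none to reproduce. The yardstick itself is not stable: 7.1 states 0.08 in the text, but its printed formula divides by 0.05 squared. I use the stated 0.08 and give the 0.05 equivalent once.

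**Inputs not in the documents (assumed, shown as ranges).** The cancer share π among suspected patients, the biopsy miss rate f, and the probability q that a missed cancer is FAPI-positive.

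**Step 1. Formula.** Let x be the number of missed cancers per true non-cancer: x = f·π/(1 − π), if every cancer rests on biopsy alone. Missed cancers join the reference-negatives, so

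apparent specificity = [0.96 + (1 − q)·x] / (1 + x), and loss = (q − 0.04)·x / (1 + x).

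Specificity falls whenever q exceeds 0.04. If uptake is independent of the biopsy miss, q = 0.92 and loss = 0.88x/(1 + x).

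**Step 2. When the loss reaches the allowable error.** 0.88x/(1 + x) = 0.08 gives 0.80x = 0.08, so x = 0.10: one missed cancer per ten true non-cancers. Against 0.05, 0.83x = 0.05 gives x = 0.06.

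**Step 3. The plan's own prevalence.** With π = 0.05, x = f × 0.05/0.95. At f = 10%, x = 0.0053 and specificity is 0.955. At f = 20%, x = 0.0105 and specificity is 0.951. The loss is under one point.

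**Step 4. Higher cancer shares, q = 0.92.** Apparent specificity against a true 0.96:

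| Cancer share among suspected | f = 2% | f = 5% | f = 10% | f = 20% |
|---|---|---|---|---|
| 50% | 0.943 | 0.918 | 0.880 | 0.813 |
| 70% | 0.921 | 0.868 | 0.794 | 0.680 |
| 80% | 0.895 | 0.813 | 0.709 | 0.569 |

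If only some cancers rest on biopsy alone, x shrinks in proportion. With 1.5 cancers per non-cancer:

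| Biopsy-only share | x | f = 3% | f = 10% | f = 15% |
|---|---|---|---|---|
| 60% | 0.9f | 0.937 | 0.887 | 0.855 |
| 100% | 1.5f | 0.922 | 0.845 | 0.798 |

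Three of these six values stay within 0.08 of 0.96.

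**Step 5. Relaxing independence.** Take 120 suspected patients, 70% with cancer, 5% missed. There are 84 cancers and 36 non-cancers; 4.2 cancers are missed, leaving 79.8 reference-positives and 40.2 reference-negatives. Scan-positive cancers number 84 × 0.92 = 77.28 and true negatives 36 × 0.96 = 34.56. Then specificity = [34.56 + 4.2(1 − q)]/40.2, sensitivity = (77.28 − 4.2q)/79.8, and the change in accuracy = 4.2(1 − 2q)/120.

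| q | Specificity (true 0.960) | Sensitivity (true 0.920) | Accuracy (true 0.932) |
|---|---|---|---|
| 0.92 | 0.868 | 0.920 | 0.903 |
| 0.50 | 0.912 | 0.942 | 0.932 |
| 0 | 0.964 | 0.968 | 0.967 |

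Accuracy falls when more than half of the missed cancers are FAPI-positive and rises when fewer are. Sensitivity is inflated whenever missed cancers are less often FAPI-positive than the rest.

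**The case against.** Histology from biopsy or surgery is an ordinary reference standard, and detailed adjudication rules are often left to a later document. That carries some weight, but the Protocol itself defines the standard in 5.2.2, and the point addresses what that definition admits.

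Three stronger readings are tempting and are not supported:

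- **That any biopsy result is declared final.** The text never says so. It only fails to qualify a non-malignant biopsy.
- **That a non-diagnostic sample is scored negative.** No sentence assigns it to any cell, and it is arguably not a pathological result at all.
- **That specificity will certainly fall by more than 0.08.** This needs assumed miss rates and cancer shares and a high q. At the stated prevalence the effect is small, although 5% fits a suspected-or-confirmed population badly.

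Later surgical pathology would probably be collected through the records and telephone calls, so the discordant case is partly covered. What remains is the missing precedence rule and the benign biopsies that are never followed by surgery.

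There is also a fair warning about the remedy. Benign inflammatory lesions with FAPI uptake are a natural source of genuine false positives. Removing every non-specific benign biopsy from the primary table could delete them and inflate specificity. That objection stands, and the fix allows for it.

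**Conclusion.** The concern holds in limited form. As written, 5.2.2 allows a suspected patient with a sampling-missed cancer to be counted as reference-negative, and it gives no rule when biopsy and surgery disagree. The consequence is a downward bias in specificity and accuracy if the missed tumours are mostly FAPI-positive, or inflated sensitivity if they are mostly FAPI-negative.

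The firmest statement of size is the threshold: a specificity loss of 0.08 at about one missed cancer per ten true non-cancers. It rests on the plan's sensitivity and specificity and on uptake being independent of the miss. Whether the trial would reach that threshold cannot be determined from the documents, so the figures for particular miss rates and cancer shares are illustrations, not forecasts.

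**What to change.** Amend 5.2.2 to state:

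1. Malignant histology or cytology at any time within a prespecified window is reference-positive.
2. Surgical pathology overrides biopsy when they disagree.
3. A non-malignant biopsy is confirmed reference-negative when it gives a specific benign diagnosis, or when no lung cancer is recorded over a fixed period of the existing record and telephone follow-up. The investigators should set that period in advance.
4. A non-diagnostic sample alone is not a reference result.
5. Non-malignant biopsies without the confirmation in item 3 stay in the primary table as reference-negative. Two sensitivity analyses are reported, one counting them as reference-positive and one excluding them.

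Section 5.3.3 on loss to follow-up, which removes lost patients from the diagnostic analysis, needs a matching sentence. Otherwise a patient with a biopsy result could be dropped only because the confirming contact failed, contrary to item 5.

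These rules classify data and change no patient's care. The cost is more than wording: the telephone contact, now limited to obtaining pathology, must also ask about any later lung cancer diagnosis, and some classifications wait until the window closes. The rules should be fixed before results accrue, because reading is unblinded.

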5.3 Subject Selection

5.3.1 Eligibility Criteria for Subjects

- (1) Patients with suspected or confirmed lung cancer
- (2) 18F-FAPI PET/CT has been performed.

5.3.2 Exclusion Criteria for Subjects

- (1) Concurrent presence of other active malignant tumors or a history of other malignant tumors within the past 5 years;
- (2) Severe uncontrollable diseases or active infections;
- (3) Ineligible participants for informed consent.
- (4) Pregnant and lactating women.

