5.3.3 Criteria and Procedures for Subject Withdrawal from the Study

Clinical trial personnel will collect medical history and verify the inclusion/exclusion criteria of subjects through the hospital's electronic medical record system. Subjects who do not meet the study requirements based on their personal conditions will not be approved to participate in the study.

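### The infection and other-malignancy exclusions carry no reference date and are checked after the scan, so they can screen out reference-negative, possibly false-positive, patients

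*Protocol*

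**What the plan says.** Section 5.3.1 has two inclusion criteria: "Patients with suspected or confirmed lung cancer" and "18F-FAPI PET/CT has been performed". Section 5.3.2, repeated in 4.2 and the summary, excludes (1) "Concurrent presence of other active malignant tumors or a history of other malignant tumors within the past 5 years" and (2) "Severe uncontrollable diseases or active infections". Neither exclusion states a reference date, and the five-year look-back in (1) has no anchor.

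Under the heading on subject withdrawal (one of two sections numbered 5.3.3), staff are to "verify the inclusion/exclusion criteria of subjects through the hospital's electronic medical record system". The consequence is this: "Subjects who do not meet the study requirements based on their personal conditions will not be approved to participate in the study".

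Section 6.2 puts consent first. It continues: "Subsequently, eligible subjects are screened from the target population according to the pre-established inclusion and exclusion criteria". The only time window nearby, "within one week prior to the signing of the informed consent form", governs baseline data collection, not the exclusions. The history taken at that stage includes recent pathology. Section 5.2.2 makes biopsy or surgical pathology the reference standard, and 5.2.1 states that there is no blinding. The summary also describes enrolling patients and then following up their pathology.

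**The concern.** In a diagnostic accuracy study, eligibility should not depend on the reference result. Here the scan comes before the eligibility check, and the pathology may already be in the record when the check is made. Nothing limits the exclusions to what was known before the scan.

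Take a suspected patient with a FAPI-positive lung lesion whose biopsy, already reported, shows an infection. The record now shows an active infection, and exclusion (2) can be applied. That patient is reference-negative for lung cancer, and the scan is a false positive. If the patient is refused entry, the case never reaches the specificity denominator.

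Specificity and accuracy are primary endpoints (sections 2.1 and 5.4), and PPV is listed in 7.3. At patient level, confirmed cases are reference-positive, so reference-negatives can come only from the suspected patients. Three centres could also apply an undated rule differently. A patient who was never enrolled cannot be recovered at analysis.

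**Working it through.** The protocol states no figure on this point, so there is none to reproduce. The check has two parts.

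**1. What the text permits**

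| Question | Protocol | Consequence |
|---|---|---|
| Is the scan done before eligibility is settled? | 5.3.1: a completed scan is required | Yes |
| Where is eligibility checked? | 5.3.3 (withdrawal): electronic record, no cut-off date | Anything on record can count |
| Can pathology be known by then? | 6.2: recent pathology is part of the history | Yes, for some patients; the number is not stated |
| Are the exclusions limited to conditions known before the scan? | 5.3.2, 4.2: no date | No |
| What follows from failing a criterion? | 5.3.3 (withdrawal): not approved to participate | Refusal at entry |
| Can pathology arrive after enrolment? | Summary: enrol, then follow up pathology | Yes, and no text then removes the case |

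The selection is therefore possible at entry, when pathology is already in hand. It is not a stated rule after entry.

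**2. What it could do to specificity**

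Section 7.3 defines specificity as TN/(TN + FP). Let f be the share of false positives refused entry and g the share of true negatives refused entry. The reported value is then

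Sp' = TN(1 − g) / [TN(1 − g) + FP(1 − f)].

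All inputs here are assumptions. Section 7.1 lists a prevalence of 0.05, but its printed formula does not use it, and it does not say how many reference-negatives would be infections. I use 30 reference-negatives; that number cancels, so only the true specificity, f and g matter.

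With true Sp = 0.80, TN = 24 and FP = 6:

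- f = 0.50, g = 0: 24/(24 + 3) = 0.889
- f = 0.50, g = 0.25: 18/(18 + 3) = 0.857
- f = 0.50, g = 0.50: 12/(12 + 3) = 0.800, no bias

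Over a range of true values with g = 0:

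| True Sp | f = 0.25 | f = 0.50 | f = 0.75 |
|---|---|---|---|
| 0.70 | 0.757 | 0.824 | 0.903 |
| 0.80 | 0.842 | 0.889 | 0.941 |
| 0.90 | 0.923 | 0.947 | 0.973 |

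A second view of the same effect: suppose k of the 30 lesions prove to be infection and all k are refused entry. Specificity is s among those k and 0.85 among the rest, so true Sp = [k·s + (30 − k)·0.85]/30.

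| k | s = 0.60 | s = 0.40 | Reported |
|---|---|---|---|
| 3 | 0.825 | 0.805 | 0.85 |
| 6 | 0.800 | 0.760 | 0.85 |
| 9 | 0.775 | 0.715 | 0.85 |

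If s is also 0.85, true and reported specificity agree. The cost is then the loss of 3/30 to 9/30, or 10% to 30%, of the reference-negatives.

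Equal rates remove the bias in specificity only. PPV is TP/(TP + FP), so it rises whenever false positives are dropped and true positives are kept. Accuracy also shifts with the balance of positive and negative cases.

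**The case against.** The strongest reply is that these are ordinary comorbidity exclusions. In criterion (1), the words concurrent and other point to a cancer alongside the lung cancer, not to an alternative diagnosis of the study lesion. In criterion (2), the opening adjectives may also qualify infections, which would narrow it. Pathology is often obtained after enrolment, for some patients by telephone, so it would not be in the record at screening. Scan-negative infections would be excluded too, and the protocol has no FAPI uptake figures for infection, so the direction of any bias is assumed.

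Much of this stands. The comorbidity reading of (1) is the more natural one, and the direction and size are not established. It does not settle criterion (2): the wording does not say whether an infection that turns out to be the scanned lesion counts, or as of when.

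A reader might go further in two ways that the protocol does not support.

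- **Removal after enrolment.** One might infer it from the heading on subject withdrawal. The text under that heading concerns only verification and refusal at entry, and no sentence removes an enrolled patient when later pathology shows infection or another cancer.
- **Other cancers as lost false positives.** Section 2.1 sets the target as lung cancer, but the image criteria in 6.2 treat a positive scan as a sign of malignancy in general. Under the second target, a FAPI-positive lymphoma or metastasis would be a true positive. Infection is reference-negative under either target.

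**Conclusion.** The point holds for entry to the study. Exclusions (1) and (2) are undated, are applied after the scan from a record that may already contain the pathology, and are applied without blinding. A suspected patient with biopsy-proven infection in the scanned lesion can be refused entry, and a reference-negative, possibly false-positive, case is then lost.

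Specificity would be overstated only if false positives are refused at a higher rate than true negatives, that is, if the refused cases are scan-positive more often than other reference-negatives. The protocol gives no case mix, so the size is unknown. Under the assumed inputs, the effect on specificity runs from nothing to about 0.20 (0.70 reported as 0.903). It would be wrong to say that specificity is overstated as a matter of fact, or that the plan removes enrolled patients on their biopsy result.

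This is more than detail left to an analysis plan, because eligibility is fixed in the protocol.

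**What to change.** - In 5.3.2 and 4.2, state that exclusions (1) and (2) refer to conditions documented before the 18F-FAPI scan, and that the diagnosis later established for the scanned study lesion is not a ground for exclusion.
- In 5.3.3 (withdrawal), state that diagnostic information obtained after the scan does not remove a patient from the diagnostic analysis.
- On the screening log, record the date of each excluding diagnosis.
- State one target condition, reconciling 2.1 with the image criteria in 6.2. Count infection in the study lesion as reference-negative, and classify non-lung malignancy according to that target.

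The cost is a few sentences and one log field, best added before or early in the recruitment period (October 2025 to October 2028). The downside is that reported specificity may be lower.
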